### **6.4 Study Specific Tolerance for Inclusion/Exclusion Criteria**

Subjects who fail to meet one or more of the inclusion criteria or who meet any of the exclusion criteria will not be enrolled in this study. Waivers of any of the above study entry criteria will not be granted.

### **6.5 Screen Fail Criteria**

Any consented patient who is excluded from the study before randomization is considered a screen failure. All screen failures must be documented with the reason for the screen failure adequately stated. Screen failures will not be re-screened for this study.

## **7 STUDY PROCEDURES**

### **7.1a Recruitment from collaborating urology clinics**

Clinic study staff will identify potential eligible participants from urologic clinics at the University of Washington, Valley Medical Center and the Veterans Affairs Seattle Puget Sound Health Care System. Clinic study staff will pre-screen men to determine medical eligibility. Recruitment efforts will be targeted towards medically eligible men living in the greater Seattle area. All of our recruitment messages will outline the parameters of the project and will stress the time commitment necessary in order to participate. UW, Valley and VA clinic staff will approach eligible prospective participants to tell them about the study. Interested men will be provided a study brochure, and will be asked to sign consent to allow their personal contact information to be reported to FHCRC study staff for formal recruitment.

### **7.1b Recruitment from community urology clinics**

If a patient from outside UW, Valley and VA contacts study staff directly about participating, PALS study staff will first obtain authorization (HIPAA) to allow access to the patients' medical records to confirm medical eligibility requirements are met before completing the final eligibility screening. FHCRC study staff will contact eligible and interested men by phone to further review the study procedures, and to conduct the final eligibility screening verbally. Men who meet all eligibility requirements and agree to participate will be scheduled to attend Visit 1 at the FHCRC Prevention Center clinic.

### **7.1c Recruitment from CSS**

Direct case recruitment from CSS will follow the IRB-approved “Cancer Surveillance System Protocol for Direct Case Recruitment”. Briefly, CSS will identify potential case participants and notify study staff. We will contact local urologists known to the study PI to first determine whether potential case patients meet the study eligibility requirements. Potential case patients who are known to not meet the study eligibility requirements will not be contacted. Potential case patients will be sent a ‘Prior Notification’ letter that describes the CSS, informs them that they are being invited to participate in PALS. Included with this letter is a letter from the PALS study team and a study brochure introducing the PALS study. After 10 days, if a potential case participant has not opted out of contact and there is no evidence to suggest that the prior notification letter could not be delivered; PALS study staff will contact the potential case participant. During this call, PALS study staff will introduce the PALS study, review study procedures and to conduct a verbal eligibility screen. Men who are interested in participating and meet the eligibility requirements will be asked to sign and return a HIPAA authorization to allow access to medical records to confirm medical eligibility. Once these procedures are complete, potential case participants will be scheduled to participate in the study.

## 7.2 Consent

A waivers of HIPAA authorization has been obtained to allow the University of Washington and the Veterans Affairs Seattle Puget Sound Health Care System urology clinic study staff to pre-screen patients for eligibility. Clinic study staff will obtain informed consent from medically eligible and interested men to allow their personal contact information to be sent to the FHCRC for recruitment into this study.

Men who self-refer to the study (from outside the VA/UW/Valley health care systems) or who are recruited via CSS will be asked to sign a HIPAA authorization to allow access to medical records to confirm medical eligibility to participate in PALS.

Eligible men will be asked to sign the study I consent to participate in the intervention trial at clinic visit 1. Participants who are recruited from UW/VA/Valley will also complete a HIPAA authorization to allow access to the medical information required to meet study objectives (Participants who self-refer to the study or who are recruited via CSS will already have signed the HIPAA authorization prior to Visit 1).

## 7.3 Randomization

Participants will be randomly assigned to either the intervention or control arm using a computerized program. In order to evenly distribute men to treatment arm, randomization will be blocked on BMI (25-29.9 or 30+) and age (<65years or 65+).

## 7.4 Intervention

**Intervention.** The DPP intervention entails both a dietary program and an exercise component with goal based behavioral teaching. The goal is for participants to lose 7% total body weight over a 6 month time period at a pace of 1-2 pounds per week. Participants will be weighed at the start of each session. The program involves 16, 30-minute to one-hour sessions led by a dietitian over a 24-week period. Each session has a curriculum for the lifestyle coach/dietitian

(<http://www.cdc.gov/diabetes/prevention/recognition/curriculum.htm#3>). These sessions are designed to help the patient adopt, and reinforce, lifelong skills for healthy living. The structured sessions provide training on nutrition, physical activity and behavioral self-management. Over the first 8 sessions, the focus is on teaching the fundamentals of energy intake modification and increasing energy output while learning self-monitoring skills. The last 8 sessions focus on the social, psychological and motivational hurdles to maintain these healthy lifestyle skills. During months 6-12, intervention participants will receive a monthly newsletter to keep them engaged in the study and actively trying to achieve or maintain their weight loss goal. These newsletters will build upon the diet instruction participants received during the first 6 months of the study.

**Diet and exercise arm.** The diet and exercise intervention is a caloric reduction program aimed at helping participants reduce total intake by 500-1000 calories/day, depending on one's initial body weight, with no more than 25% of calories from fat, and to expend at least 700 calories a week through exercise. The DPP teaches nutrition and behavior change skills: setting calorie and fat gram goals, counting calories of foods, self-monitoring, and coping with challenges to eating behavior changes. Several tools are provided, such as graphs for monitoring weight, participant worksheets, cooking and shopping for lower-fat eating, and etc. Participants

will attend 11 sessions with a study dietitian during the first 6 months of the study (once a week for 4 weeks, then every other week for 8 weeks, then once a month for 3 months) to receive diet and exercise instruction. If necessary, diet instruction can occur via telephone. During each session the dietitian will weigh the participant (or ask the participant to weigh themselves), collect and review calorie-count and physical activity journals, review the participant's dietary changes from the previous week and discuss any issues that may have arisen, providing appropriate behavioral counseling. The intervention will be individualized to the person's dietary preferences. It is important to note that the DPP curriculum includes lessons related to compliance, retention and motivation.

Supervised exercise. In addition, participants will complete up to 24 exercise sessions under the supervision of an exercise physiologist. The first two sessions will be one on one with the exercise physiologist to introduce exercises and provide teaching. The subsequent weekly visits will be supervised, but not one on one. If necessary, exercise instruction and supervision can via telephone. Many of the exercise sessions will coincide with the dietitian sessions.

Exercise test. All participants will undergo a submaximal graded exercise treadmill test (GXT) to 85% predicted heart rate reserve at baseline and at 6 months. The purpose of the GXT is to measure fitness level (predicted aerobic capacity), establish exercise heart rate for training, and ensure safety of exercise training. A screening questionnaire will be administered prior to the GXT to determine whether any contraindications to exercise testing are present. A brief heart and lung exam will also be conducted and the resting ECG reviewed. There will be physician on-call for all of these procedures.

Heart rate monitor. Participants randomized to the diet and exercise group will be asked to wear a heart rate monitor during exercise sessions for one week a month. They will be asked to put the monitor on prior to their daily exercise session. At the end of the exercise session (on average about 30 minutes) they will record the maximal heart rate that appears on the monitor screen. Men in the control group will not wear the heart rate monitor. This tool will allow participants to monitor their exercise intensity with an individual heart rate range, provided by the exercise physiologist based on the GXT, to stay in while they exercise. This will help to ensure that the participant exercises at an appropriate intensity level. We have chosen to use heart rate monitors because they measure kcals and time in activity directly as heart rate increases linearly with activity intensity. Heart rate monitors are also ideal to use for this intervention because they yield data on the time in specific heart rate zones during exercise and sedentary time. This approach will allow us to directly measure number of minutes/week (goal = 150 minutes/week) and whether individual goals are being met. The heart rate monitor data will be downloaded to the study database.

Compliance. Compliance to dietary and physical activity goals will be evaluated both formally and informally. The primary formal tool to assess overall study compliance will be participant weight loss; weight will be measured at each session (using a research scale and a standardized protocol) and if participants are meeting weight loss goals then compliance is achieved. Other formal compliance tools to assess compliance will include study dietitian-directed proactive check-ins and completion of a 3-day diet record (at 6 mo). At each intervention session the dietitian will review progress and any potential barriers, and individual dietary goals will be adjusted as needed. Formal measures for adherence to physical activity goals will include reviewing heart rate monitor data and formal check-ins with the exercise physiologist. Informally, compliance to diet, physical activity and weight loss goals will be assessed by self-monitoring through logs and journaling. In addition, global-study wide tailored messages with diet, physical activity and behavioral strategies content will be delivered by text message and e-blasts. This multi-tiered approach has been shown to maximize adherence and retention during intervention trials.

**Controls.** Written information on standard healthy lifestyle recommendations will be provided along with a 20-30 minutes individual session with a dietitian including 1) US Dietary Guidelines ([www.dietaryguidelines.gov](http://www.dietaryguidelines.gov)); 2) Activity goal of 30 minutes of physical activity 5 days/week; and 3) Discussion of the health benefits of weight loss along with general behavior change suggestions for weight loss.

Follow-up Visits. All participants will come to the Fred Hutch Cancer Prevention Center for study visits at baseline (0), 3, 6 and 12 months. A description of the clinical assessments performed at each follow-up visit is provided below.

## 7.5 Clinical Assessments

Study visits will occur at baseline, 3, 6 and 12 months. During study visits, participants will undergo anthropometrics, fasting blood studies and/or complete physical activity, food diaries and HRQOL questionnaires. Assessments at 6 months will be used to evaluate the effectiveness of the intervention, and at 12 months will evaluate maintenance of the intervention.

Anthropometric Measurements. Height will be measured at baseline only, and weight, waist (1" above umbilicus), hip circumferences will be measured at baseline, 3, 6 and 12 months. Dual x-ray absorptiometry (DXA) using a GE Lunar iDXA will be obtained to measure overall percent body fat, lean mass and total bone density at baseline and 12 months.

Twelve-hour fasting blood. Fasting blood samples will be collected at baseline, and at 3, 6, and 12 months. Vacutainers will be labeled with participants' study ID and date, processed within 1 hour of collection and stored at -70°C.

Prostate Tissue. As part of the consent to participate in this study, participants are asked to give permission to investigators to allow a) the collection of two extra prostate biopsy cores during their standard-of-care biopsy (UW and VA participants only), and b) access to pathology tissue from a pre-study biopsy (that was already collected as part of routine medical care for diagnostic purposes) to be used for this study (UW and VA participants only). For VA patients, separate consent allowing the collection of extra biopsy cores during a standard-of-care biopsy, and allowing access to biopsy tissue after used for diagnostic purposes will be obtained at the VAPSHCS by VA study staff on the day of their scheduled biopsy. For participants who are not patients at UW or the VA, since the collection of extra biopsy cores is not possible, they will be asked to sign a separate "Release of Information" allowing access to prostate biopsy tissue collected as part of their routine care. Tissue blocks, fixed in formalin and embedded in paraffin (standard for AS biopsies), will be sent to [name] laboratory. Participants will be enrolled on study so that the intervention calendar coincides with routine clinical care; no extra biopsies will take place outside of the routine clinical care. Tissue blocks will be cut and sections mounted on charged slides.

### Questionnaires (see Appendix).

Food Diary. All participants will complete a 3-day food diary at baseline and 6 months. For men in the diet and exercise arm, the baseline food diary will be used together with information on the participant's body weight, age and usual physical activity level to calculate usual energy intake using the Nutrition Data Systems for Research (NDS-R, University of Minnesota Nutrition Coordinating Center, version 2012). The study dietitian will then compute the average calorie reduction needed to meet study goals individualized for each participant. This calorie level will be explained to each participant as incorporated into the DPP curriculum. At the end of the 6 month intervention, all participants will again complete a 3-day food diary to assess compliance.

Physical Activity. Physical activity will be assessed at baseline and 6 months with a self-administered administered physical activity questionnaire, the Arizona Activity Frequency Questionnaire (AAFQ) (see appendix). The AAFQ is a 59-item scannable questionnaire. The AAFQ has been validated in an eight-day doubly labeled water protocol to measure total energy expenditure. It has been upgraded with the compendium of physical activity codes and MET intensities. The AAFQ categorizes physical activity by leisure, recreational, household, and "other" activity categories. At randomization the AAFQ will assess participants' baseline activity level. These baseline data will inform the types of exercises that the exercise physiologist will prescribe for each participant to meet the intervention physical activity goal of >150 minutes/week of at least 700 kcal of physical activity.

Lifestyle. Demographics, lifestyle habits and family history of prostate cancer will be assed at baseline only. Self-assessments of Lower Urinary track symptoms will be completed by participants at baseline, 3, 6, and 12 months, and medication use will be completed at baseline, 6 and 12 months..

**Quality of life.** Self-administered quality of life (QOL) questionnaires will be completed by participants at baseline, 3, 6 and 12 months. We will assess the following: 1) anxiety related to PCa with the *Memorial Anxiety Scale for Prostate Cancer (MAX-PC)*; 2) PCa-specific QOL with the *Expanded Prostate Cancer Index (EPIC) Short Form*; and 3) generic QOL with the extensively validated EQ-5D-5L.

## 7.6 Outcomes

### **Serum Biomarkers.**

**Glucose.** Plasma glucose concentrations will be measured in duplicate by an automated glucose oxidase method using SVR glucose test (Behring Diagnostics) Glucose assays will be performed in the Diabetes Research Lab.

**Insulin.** Insulin concentration will be determined using an immunoenzymatic assay as per manufacturer's instructions (Invitrogen). Insulin assays will be performed in the Diabetes Research Lab.

**C-peptide.** C-peptide is the cleaved sub-unit of pro-insulin. Levels will be quantified using a solid phase sandwich-type ELISA as per the manufacturer's protocol. The assay uses monoclonal antibodies directed against distinct epitopes of C-peptide (Beckman Coulter). C-peptide assays will be performed in [name] lab.

**IGF-1.** IGF-1 levels are quantified using a solid phase sandwich-type Enzyme Linked-Immuno-Sorbent Assay (ELISA) as per the manufacturer's protocol. The assay uses monoclonal antibodies directed against distinct epitopes of IGF-1 (R&D Systems). IGF-1 assays will be performed in [name] lab.

**IGFBP-3.** IGFBP-3 levels will be quantified using in vitro enzyme-linked immunoabsorbent assays following manufacturer's protocol (RayBiotech). IGFBP-3 assays will be performed in [name] lab.

**Adiponectin.** Adiponectin is quantified using in vitro enzyme-linked immunoabsorbent assays following manufacturer's protocol (RayBiotech). Adiponectin assays will be performed in [name] lab.

**Tissue Biomarkers.** pIR/IR, pIGF-IR/IGF-IR and pAKT/AKT protein expression will be assessed by IHC. Sections will be rehydrated and incubated with 3% H2O2, blocked with avidin/biotin blocking solution (Vector Laboratories Inc.) and then 5% goat serum. The sections will be incubated with either rabbit anti-IGF-1R $\alpha$  (1:100; Santa Cruz Biotechnology), rabbit anti-phospho-IGF-1R (1:50; Abcam), mouse anti-insulin receptor (1:100; Santa Cruz Biotechnology), rabbit anti-phospho-insulin receptor (1:50; Abcam), rabbit anti-AKT, rabbit anti-phospho-AKT (1:50; Cell Signaling) or rabbit or mouse control IgG at the same concentration, washed and incubated with biotinylated secondary antibody (1:100; Santa Cruz Biotechnology), developed using the Vectastain ABC kit (Vector Laboratories Inc.) and stable DAB (Vector Laboratories), counterstained with hematoxylin, dehydrated, and mounted with Permount (Fisher). All staining will be performed in [name] laboratory. A research pathologist will score the staining and be blinded to intervention arm. Blind duplicates (5%) will be included. IHC staining intensity for each tissue section will be determined as follows: 0=no staining, 1=faint/present staining, 2=strong/intense staining. The percentage of staining cells is then estimated and a composite score calculated by multiplying mean intensity score and percent cells stained positively, and then dividing by number of cores taken.

**Pathologic Features.** Pathologic findings will be recorded from the baseline and post-intervention biopsies, including Gleason grade, number of cores taken (12 core biopsy is standard); number of cores with cancer, and the percentage of each core involved with cancer. Adverse pathology on surveillance biopsy will be indicated by any of the following: a  $\geq 1$  pt increase in Gleason grade, an increase to  $> 50\%$  of any one core involved with cancer, and/or an increase in the number of cores involved with cancer.

**Intervention Sustainability.** Participants will return to the clinic 6 months after the active intervention ends to assess whether they have continued to follow the lifestyle intervention on a long term basis. Additional measures of blood glucose, weight and quality of life will be assessed.

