### 11.1 Sample Size and Randomization

Our power calculations give the minimally detectable intervention effects for endpoints in Primary Specific Aims, setting two-sided alpha error at 5% and power at 80%. We have set a sample size of 100 in each of the intervention and control arms, based both on our overall evaluation of minimum detectable differences across the range of study endpoints and on a reasonable estimate of the number of men we can recruit. The sample size allows for a drop-out rate of 5%, and power calculations assume correlations of 0.70 between baseline and follow-up measures.

Table 4 gives the minimally detectable differences between treatment arms for serum and tissue biomarkers of glucose regulation. We have used a variety of data sources to complete these tables, attempting whenever possible to use data generated from human studies. For serum biomarkers of glucose regulation, we use data from our own pilot study and the PCPT, and for tissue expression of IR/IGF-R1 and AKT we use data from Cox et al. The minimum detectable intervention effects range from 5.3% for serum glucose to 33.1% for insulin. Previous studies have shown that dietary change can induce the following intervention effects: 7% for fasting glucose, 40% for insulin and 2.2 % for adiponectin. Our pilot study based on the DPP demonstrated an intervention effect of ↑9.7% for IGFBP3, ↓38% for insulin and ↓14% for C-peptide. Based on these observations, we will have good power to detect changes in all serum biomarkers of glucose regulation, consistent with those seen in other human intervention studies.

For expression of IR, IGF-1R and AKT on surveillance prostate biopsies, the minimum detectable intervention effects are 29.2%, 46.3% and 26.5%, respectively. Previous experimental studies in animals have

**Table 4. Minimal detectable differences in serum and tissue biomarkers at 80% power,  $\alpha=0.05$  given a sample size of 200 (100 in each of the lifestyle intervention and control arms)**

Biomarker	Baseline Mean (SD) or n (%)	Minimum Detectable Difference (MDD)	
		Mean	% of mean
Primary Aim 1 - Serum			
Fasting glucose, mg/dL	106.3 (12.6)	5.6	5.3%
Primary Aim 2 - Serum			
C-peptide, ng/mL	1.7 (1.2)	0.54	31.6%
Insulin, pmol/L	138.0 (102.0)	45.7	33.1%
IGF-1, ng/mL	232.7 (75.4)	33.8	14.5%
IGF-BP3, ng/mL	4317.6 (975.2)	436.5	10.1%
Adiponectin, ug/mL	6.1(3.9)	1.8	29.0%
Primary Aim 3 – Tissue			

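### The Aim 3 tissue score as worded in 7.6 cannot produce Table 4's planning values and varies with the number of cores; separately, 4.1 dates the biopsies differently from the synopsis, 5.1 and 11

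*Combined protocol and SAP*

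**What the plan says.** **Score.** Section 7.6 (Tissue Biomarkers) grades intensity as "0=no staining, 1=faint/present staining, 2=strong/intense staining" and introduces the grading with "IHC staining intensity for each tissue section will be determined as follows". The percentage of staining cells is then estimated, and the composite is formed by "multiplying mean intensity score and percent cells stained positively, and then dividing by number of cores taken". Under Pathologic Features, the same section records the "number of cores taken (12 core biopsy is standard").

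**Planning values.** Table 4 in 11.1 gives baseline mean (SD) and minimum detectable difference (MDD) as follows: insulin receptor 30 (34) and 13.9; IGF-1 receptor 112 (80) and 32.7; AKT 128 (83) and 33.9. The tissue values come from a published external data set. No unit is given, and nothing links them to the 7.6 score. The section also states that "power calculations assume correlations of 0.70 between baseline and follow-up measures".

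**Which cores.** Section 7.5 provides for "the collection of two extra prostate biopsy cores during their standard-of-care biopsy (UW and VA participants only") and, for baseline, "access to pathology tissue from a pre-study biopsy (that was already collected as part of routine medical care for diagnostic purposes"). It does not say whether the extra cores count as taken. Under 7.3, "randomization will be blocked on BMI (25-29.9 or 30+) and age (<65years or 65" or over); recruiting clinic is not a factor.

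**Biopsy dates.** Section 4.1 says that the yearly biopsies coincide with the start and end of the 12 months of follow-up after randomisation. The synopsis, 5.1 and 11 place the baseline biopsy about 6 months before randomisation and the follow-up biopsy 6 months after it.

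**The concern.** The divisor puts the endpoint on a scale that Table 4 cannot share. Two analysts following 7.6 could therefore compute different values for a primary-aim endpoint, and only some readings agree with the trial's own planning figures. Taken literally, the score also measures in part how many cores were sampled. The pre-study biopsy predates enrolment, so any extra cores enter only at follow-up and their effect does not cancel from the change score.

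The date conflict is a separate matter. One dating puts the follow-up tissue at the end of the 6-month intervention; the other puts it 6 months after the intervention ends. These are different questions about the intervention, and section 11 regresses tissue expression on glycaemic measures at 6 months.

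**Working it through.** **1. Reproduce Table 4.** Inputs from 11.1: two-sided alpha 5%, power 80%, 100 per arm less 5% drop-out = 95 per arm. A two-sample t-test then needs a standardised difference of 0.4086.

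| Marker | 0.4086 x SD | Table 4 MDD | With correlation 0.70: x √(2 - 2 x 0.70) = √0.6 |
|---|---|---|---|
| IR | 13.89 | 13.9 | 10.8 |
| IGF-1R | 32.69 | 32.7 | 25.3 |
| AKT | 33.91 | 33.9 | 26.3 |

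This shows two things. First, 34, 80 and 83 were used as SDs, so the column's alternative label of n (%) does not apply to these rows. Second, the MDDs correspond to an SD of change equal to the baseline SD, which is a correlation of 0.5 and not the stated 0.70. Both correlations are carried below.

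**2. Range of the literal score.** Maximum = 2 x 100 / cores. At 12 cores this is 200/12 = 16.7, and at 14 cores 200/14 = 14.3. The largest SD of a variable bounded on 0 to M is M/2, so at 12 cores it is 8.3. All three Table 4 means exceed 16.7 and all three SDs exceed 8.3. The IGF-1R and AKT MDDs (32.7, 33.9) exceed the whole range. The IR MDD of 13.9 lies below 16.7 but derives from the infeasible SD of 34.

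**3. Range without the divisor, or with a per-core average.** The score runs 0-200, and the largest SD at mean m is √(m(200 - m)).

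| Mean | Largest possible SD | Table 4 SD |
|---|---|---|
| 30 | 71.4 | 34 |
| 112 | 99.3 | 80 |
| 128 | 96.0 | 83 |

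All three pairs are feasible. This is a bounds check; it does not prove that 0-200 is the scale of the source data.

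**4. Constant divisor.** Dividing every score by 12 divides the effect and the SD alike. The standardised difference, and hence power, is unchanged.

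**5. Varying divisor.** For 14 against 12 cores with identical staining, 12/14 - 1 = -14.3%. Assume that baseline has 12 cores, that the extra cores count at follow-up, and that 95 men per arm are scored. Put k = 12/14 = 0.857. On the 12-core equivalent, with every man affected, the effect becomes k x MDD and the SD of change becomes SD x √(1 + k² - 2rk), where r is the correlation. For IGF-1R:

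| | r = 0.5 | r = 0.70 |
|---|---|---|
| No man affected: standardised difference | 32.7/80.0 = 0.409 | 32.7/61.97 = 0.528 |
| Power | 80% | 95% |
| All men affected: standardised difference | 28.03/74.94 = 0.374 | 28.03/58.50 = 0.479 |
| Power | 73% | 91% |

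IR and AKT at their own MDDs agree within 1 point. The UW/VA share is not in the documents. With half the men affected, IGF-1R power is about 76% (r = 0.5) or 93% (r = 0.70). In simulation with half or all of the men affected, type I error was 4.7-5.3%.

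**6. Dates side by side.** Section 4.1 implies about month 0 and month 12. The synopsis, 5.1 and 11 say about month -6 and month +6. Both intervals are 12 months; they differ in where they sit relative to randomisation and the 6-month intervention. Fig. 3, which 4.1 and 11 cite, was not available, and the visit timeline in 4.1 could not be read reliably.

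**The case against.** The best defence is that the divisor loosely describes an average. Section 7.6 scores each tissue section, and averaging over cores is the natural reason to divide by their number. That gives 0-200, where Table 4 is feasible and the mechanical dependence on core count disappears. This stands as a plausible intent. The text does not settle it, however: it already uses a mean intensity before dividing, and it divides by cores taken, whereas 5.1 concerns cancer cells, which benign cores do not contain.

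It is also fair to say that the tissue values come from outside data on an unstated scale, and that research cores need not count as taken; then the loss in step 5 is zero. At the stated 0.70, even the worst case keeps about 91% power at Table 4's MDD.

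Three stronger conclusions may tempt a reader, and the documents support none of them:

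- **Aim 3 is underpowered.** The scale mismatch does not show this, because a constant divisor leaves power unchanged.
- **The extra cores bias the arm comparison.** Allocation is random, so UW/VA men are expected equally in both arms. Not blocking on clinic leaves chance imbalance, which is noise.
- **The apparent within-arm fall in staining invalidates the Aim 3 test.** Section 11 tests only whether change differs between arms, so a shift common to both arms bears on no planned Aim 3 test.

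The defence of the score does not touch the date conflict. Fig. 3 may show which dating was intended, but the written sections would still disagree.

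**Conclusion.** The point holds as a defect of definition. Confidence is high that the literal 7.6 score and Table 4's tissue values are on different scales, and medium on which formula was intended.

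The cost of the varying divisor is conditional. It needs a literal divisor, extra cores that count as taken, a 12-core baseline and an unknown UW/VA share. Its upper limit, with all men affected, is a fall from 80% to 73% at correlation 0.5 or from 95% to 91% at 0.70. These powers also assume 95 scored men per arm. A man with no cancer at follow-up has no cancer-cell score under 5.1, so they serve to compare scoring rules and are not forecasts for Aim 3.

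The date conflict is plain in the text, subject to Fig. 3, and independent of the scoring question. The passages must be reconciled; this review does not say which dating is right.

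**What to change.** 1. In 7.6, remove the division by number of cores, or replace it with an explicit average of the per-core (or per-section) products of intensity and percent positive, so that the score runs 0-200 and does not depend on how many cores were sampled.
2. State which cores enter the average, including whether the two extra UW/VA cores do. Restricting it to cancer-bearing cores would be in line with 5.1, but that is the sponsor's choice and not a necessary correction.
3. Confirm that Table 4's tissue means, SDs and MDDs are on the stated scale, or restate them.
4. Reconcile 4.1 with the synopsis, 5.1 and 11 on when the two biopsies fall relative to randomisation, and match the timing of the glycaemic measure in the Aim 3 regression to the reconciled date.

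The cost is wording and a check of units. No visit or biopsy is added, and 7.6 already records the numbers of cores taken and of cores with cancer. Averaging over cancer-bearing cores would also require the pathologist to record a score for each such core. The scoring rule should be settled before any slides are scored.
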